## 6.7. Procedures

The safety and tolerability of DSP-7888 Dosing Emulsion in combination with immunotherapy PD-1 inhibitors will be assessed for the duration of study treatment and follow-up. Refer to [Table 7](#), [Table 8](#), and [Table 9](#) for the respective schedules of assessments. Adherence to the study

design requirements, including those specified in the Schedule of Assessments is essential and required for study conduct.

**Table 7: Schedule of Assessments (Arm 1, Combination of DSP-7888 Dosing Emulsion and Nivolumab [14-Day Study Cycles])**

Tests and Procedures	Pre-Screening	Pre-Study Evaluation	On-Study Evaluations a									End of Treatment	Follow-Up For OS
			Cycle 1		Cycle 2		Cycle 3	Cycle 4	Cycle 5	Cycle 6	Cycle 7+		
Week			0	1	2	3	4	6	8	10	12+	30 days after last DSP-7888 Dosing Emulsion dose	Every 3 months after date off treatment
Day	Any time before enrollment	Within 28 days prior to first dose of study drug	1	8	15	22	29	43	57	71	85+		
Window		28 days	±2 days	±2 days	±2 days	±2 days	±2 days	±2 days	±2 days	±2 days	±2 days		
Pre-screening consent	X												
HLA-typing (A/B locus and DRB1 locus)	X												
Informed consent		X											
Inclusion/exclusion review		X											
Medical and cancer history		X											
Physical examination		X	X		X c		X c	X					
Serum pregnancy test, if applicable		X											
ECOG performance status		X			X		X	X	X	X	X	X	
Complete vital signs		X	X		X		X	X	X	X	X	X	
Body weight		X	X		X		X	X	X	X	X	X	
Hematology		X		X	X	X	X	X	X	X	X	X	
Clinical chemistry		X		X	X	X	X	X	X	X	X	X	
Thyroid function test		X			X		X	X	X	X	X	X	
Urinalysis		X		X	X	X	X	X	X	X	X	X	
Pulse oximetry		X	X		X		X	X	X	X	X	X	
Blood samples for Hepatitis B/C & HIV		X											
ECHO/MUGA		X			X			X			X d	X	
12-lead electrocardiogram		X	X e		X e			X			X f	X	
Tumor tissue samples for biomarkers g		X h									X i		
Tumor tissue samples for future biomarker analysis j		X									X i		

Tests and Procedures	Pre-Screening	Pre-Study Evaluation	On-Study Evaluations a									End of Treatment	Follow-Up For OS
			Cycle 1		Cycle 2		Cycle 3	Cycle 4	Cycle 5	Cycle 6	Cycle 7+		
Week			0	1	2	3	4	6	8	10	12+	30 days after last DSP-7888 Dosing Emulsion dose	Every 3 months after date off treatment
Day	Any time before enrollment	Within 28 days prior to first dose of study drug	1	8	15	22	29	43	57	71	85+		
Window		28 days	±2 days	±2 days	±2 days	±2 days	±2 days	±2 days	±2 days	±2 days	±2 days	+7 days b	
Blood samples for CTL induction k		X l			X m		X m		X m		X m,n	X	
Blood samples for future biomarker analysis o		X l			X m		X m		X m		X m,n	X	
Concomitant medications		X	X	X	X	X	X	X	X	X	X	X	
Adverse events p		X	X	X	X	X	X	X	X	X	X	X	
Administer DSP-7888 Dosing Emulsion			X	X	X	X	X	X	X	X	X		
Administer nivolumab							X	X	X	X	X		
Follow-up for overall survival													X q
Objective disease assessment f		X	First post-treatment assessment at Week 4 (Cycle 3), followed by one at Week 12 (Cycle 7), then 2 subsequent assessments every 6 weeks at Week 18, Week 24 (Cycle 10, Cycle 13), and finally every 12 weeks (Cycle 19 and every 6 cycles) until disease progression. s										

Abbreviations: AE = adverse event; CT = computed tomography; CTCAE = Common Terminology Criteria for Adverse Events; CTL = cytotoxic T lymphocyte; ECG = echocardiogram; ECOG = Eastern Cooperative Oncology Group; ECHO = echocardiogram; FFPE = formalin-fixed and paraffin embedded; HIV = human immunodeficiency virus; HLA = human leukocyte antigen; ICF = informed consent form; iRECIST = immune Response Evaluation Criteria in Solid Tumors MRI = magnetic resonance imaging; MUGA = multiple gated acquisition; OS = overall survival; PD-L1 = programmed death ligand 1; PET = positron emission tomography; PBMC = peripheral blood mononuclear cells; RECIST = Response Evaluation Criteria in Solid Tumors; TIL = tumor-infiltrating lymphocytes; TIS = tumor immune signature; WT1 = Wilms Tumor 1

a All tests must be performed PRIOR to injection of study treatment, with the exception of ECG.

b Complete End of Treatment assessment procedures before patient receives new anti-cancer treatment.

c Inspection of prior injection sites will be done at each administration of the vaccine.

d . From Cycle 4, ECHO/MUGA tests for ejection fraction will be done on Day 1 every 6th cycle (eg, Cycle 10, 16, 22).

e Obtained at least 2 hours post-dose of DSP-7888 Dosing Emulsion.

f From Cycle 4, 12-lead electrocardiograms will be performed on Day 1 of every 3rd Cycle (eg, Cycle 7, 10, 13).

g It should be ensured that a total of at least 23 slides of archival samples and/or the equivalent amount of archival tissue block and/or fresh biopsy samples from the enrolled patients are available. These samples must contain sufficient tumor tissue.

- h Collection of tumor tissue samples at Pre-Study evaluation is mandatory. Either archival tissue or fresh biopsy samples at Pre-study evaluation would be acceptable. Collection of fresh biopsy samples is required, if medically feasible.
- i Sample to taken at week 12 (Cycle 7), see [Section 10.1](#) for the timepoints and circumstances for tumor tissue sample collection for post treatment evaluations after Week 12 (Cycle 7). Tumor tissue samples will be collected at End of Treatment only if patient discontinues from study prior to Week 12.
- j Either archival tissue or fresh biopsy samples will be collected only after the patient signs an additional separate informed consent for these optional samples. A total of 6 to 8 slides will be sent to the central laboratory for analyses.
- l If blood is not collected at Screening, it may be obtained on Day 1 prior to administration of protocol therapy.
- m Samples to be taken pre-dosing with DSP-7888 Dosing Emulsion.
- n Sample to be taken every 2 cycles pre-dosing until dosing is discontinued (eg, Cycle 7, 9, 11, 13).
- o Additional informed consent is needed prior to collection at Pre-Study evaluation. Serum, PBMC and ctDNA (plasma) are included as a blood sample. PBMC will be prepared from whole blood at the Central Laboratory. The whole blood sample for PBMC preparation should be shipped from the clinical site to the central laboratory on the sample collection date. Blood samples for ctDNA (plasma) is collected at Screening only.
- p Use CTCAE v4.03 term, if appropriate (Note: the verbatim term should be reported, not the associated CTCAE term). All AEs must be reported for each patient from the date of ICF signature until 30 days after the last dose of study drug administration.
- q Follow-up until end of life or end of the study, whichever occur first. Follow up to occur every 3 months and/or on an ad-hoc basis for safety or regulatory purposes, or a prespecified analysis
- r Assessment consists of chest/abdomen/pelvis CT/MRI. A bone scan and MRI of the brain will be conducted when clinically indicated. Imaging technology should be consistent across the study, CT component of PET/CT assessments are sufficient to be used if PET/CT scan was done at baseline.
- s Images are assessed according to RECIST v1.1 and iRECIST.

**Table 8: Schedule of Assessment (Arm 2 of Phase 1b, Combination of DSP-7888 Dosing Emulsion and Pembrolizumab [21-Day Study Cycles])**

Tests and Procedures	Pre-Screening	Pre-Study Evaluation	On-Study Evaluations 									End of Treatment	Follow-Up For OS
			Cycle 1			Cycle 2			Cycle 3	Cycle 4	Cycle 5+		
Week			0	1	2	3	4	5	6	9	12		
Day	Any time before enrolment	Within 28 days prior to first dose of study drug	1	8	15	22	29	36	43	64	85	30 days after last DSP-7888 Dosing Emulsion dose	Every 3 months after date off treatment
Window		28 days	±2 days			±2 days			±2 days	±2 days	±2 days	+7 days 	
Pre-screening consent	X												
HLA-typing (A/B locus and DRB1 locus)	X												
Informed consent		X											
Inclusion/exclusion review		X											
Medical, cancer history		X											
Physical examination		X	X			X 			X 	X 	X 	X	
Serum pregnancy test, if applicable		X											
ECOG performance status		X				X			X	X	X	X	
Complete vital signs		X	X			X			X	X	X	X	
Body Weight		X	X			X			X	X	X	X	
Hematology		X		X	X	X			X	X	X	X	
Clinical chemistry		X		X	X	X			X	X	X	X	
Thyroid function test		X				X			X	X	X	X	
Urinalysis		X		X	X	X			X	X	X	X	
Pulse oximetry		X	X			X			X	X	X	X	
Blood samples for Hepatitis B/C & HIV		X											
ECHO/MUGA		X				X			X		X 	X	
12-lead electrocardiogram		X	X 			X 			X		X 	X	
Tumor tissue samples for biomarkers		X 									X 		
Tumor tissue samples for future biomarker analysis 		X									X 		
Blood samples for CTL induction 		X 				X 			X 		X 	X	
Blood samples for future biomarker analysis 		X 				X 			X 		X 	X	
Concomitant medications		X	X	X	X	X			X	X	X	X	

Tests and Procedures	Pre-Screening	Pre-Study Evaluation	On-Study Evaluations 									End of Treatment	Follow-Up For OS
			Cycle 1			Cycle 2			Cycle 3	Cycle 4	Cycle 5+		
Week			0	1	2	3	4	5	6	9	12		
Day	Any time before enrolment	Within 28 days prior to first dose of study drug	1	8	15	22	29	36	43	64	85	30 days after last DSP-7888 Dosing Emulsion dose	Every 3 months after date off treatment
Window		28 days	±2 days			±2 days			±2 days	±2 days	±2 days	+7 days 	
Adverse events 		X	X	X	X				X	X	X	X	
Administer DSP-7888 Dosing Emulsion			X	X	X	X			X	X	X		
Administer pembrolizumab						X			X	X	X		
Follow-up for overall survival													X 
Objective disease assessment 		X	First post-treatment assessment at Week 6 (Cycle 3), then 3 subsequent assessments at Week 12, Week 18, Week 24 (Cycle 5, Cycle 7, Cycle 9), and finally every 12 weeks (Cycle 13 and every 4 cycle) until disease progression. 										

- AE = adverse event; CT = computed tomography; CTCAE = Common Terminology Criteria for Adverse Events; CTL = cytotoxic T lymphocyte; ECG = echocardiogram; ECOG = Eastern Cooperative Oncology Group; ECHO = echocardiogram; HIV = human immunodeficiency virus; HLA = human leukocyte antigen; ICF = informed consent form; IHC = immunohistochemistry; iRECIST = immune Response Evaluation Criteria in Solid Tumors; MRI = magnetic resonance imaging; MUGA = multiple gated acquisition; OS = overall survival; PD-L1 = programmed death ligand 1; PET = positron emission tomography; PMBC = peripheral blood mononuclear cells; RECIST = Response Evaluation Criteria in Solid Tumors; TIL = tumor infiltrating lymphocytes; TIS = tumor immune signature; TMB = tumor mutational burden; WT1 = Wilms Tumor 1
- All tests must be performed PRIOR to injection of study treatment, with the exception of ECG.
  - Inspection of prior injection sites will be done at each administration of the vaccine.
  - From Cycle 3, ECHO/MUGA tests for ejection fraction will be done on Day 1 of every 4th cycle (eg, Cycle 7, 11, 15).
  - Obtained at least 2 hours post-dose of DSP-7888 Dosing Emulsion.
  - From Cycle 3, 12-lead electrocardiograms will be performed on Day 1 of every 2nd Cycle (eg, Cycle 5, 7, 9).
  - Collection of tumor tissue samples at pre-study evaluation is mandatory. Either archival tissue or fresh biopsy samples at Pre-study evaluation would be acceptable.
  - Sample to be taken at Week 12 (Cycle 5), see Section 10.1 for the timepoints and circumstances for tumor tissue sample collection for post-treatment evaluations after Week 12 (Cycle 5). Tumor tissue samples will be collected at End of Treatment only if patient discontinues from study prior to Week 12. Additional informed consent is needed prior to collection.
  - Either archival tissue or fresh biopsy samples will be collected only after the patient signs an additional informed consent for these optional samples. A total of 6 to 8 slides will be sent to the central laboratory for analyses.
  - PBMCs will be prepared from whole blood at the Central Laboratory. The whole blood sample for PBMC preparation should be shipped from the clinical site to the Central Laboratory on the sample collection date.
  - If blood is not collected at Screening, it may be obtained on Day 1 prior to administration of protocol therapy.
  - Samples to be taken pre-dosing with DSP-7888 Dosing Emulsion.
  - Sample to be taken every 2 cycles, pre-dosing until dosing is discontinued (eg, Cycle 5, 7, 9, 11, 13).
  - Additional informed consent is needed prior to collection at Pre-Study evaluation. Serum, PBMC and ctDNA (plasma) are included as a blood sample. PBMC will be prepared from whole blood at Central Laboratory. The whole blood sample for PBMC preparation should be shipped from clinical site to central laboratory on the sample collection date. Blood sample for ctDNA (plasma) is collected at Screening only.
  - Use CTCAE v4.03 term, if appropriate (Note: the verbatim term should be reported, not the associated CTCAE term. All AEs must be reported for each patient from the date of ICF signature until 30 days after the last dose of study drug administration.

15. Follow-up until end of life or end of the study, whichever occur first. Follow up to occur every 3 months and/or on an ad-hoc basis for safety or regulatory purposes, or a prespecified analysis
16. Assessment consists of chest/abdomen/pelvis CT/MRI. A bone scan and MRI of the brain will be conducted when clinically indicated. Imaging technology should be consistent across the study, CT component of PET/CT assessments are sufficient to be used if PET/CT scan was done at baseline.
17. Images are assessed according to RECIST v1.1 and iRECIST.
18. Complete End of Treatment assessment procedures before patient receives new anti-cancer treatment.

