**Table 5: PD-1 Inhibitor Dose**

PD1 Inhibitor	Dose and Schedule
Nivolumab	In Arm 1, 240 mg administered intravenously (IV) over 30 minutes ( $\pm 5$ )* every 14 days (2 weeks/cycle) starting from Day 1 of Cycle 3 (Day 29), then maintenance phase (after Cycle 3).
Pembrolizumab	In Arm 2, 200 mg/8 mL administered through IV infusion over 30 ( $\pm 5$ ) minutes every 21 days (3 weeks) starting from Day 1 of Cycle 2 (Day 22), then maintenance phase (after Cycle 2).

\*The administration time change from 60 to 30 minutes is based on the updated dosage and administration guidance of the new nivolumab product label released in July 2018.

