**Table 9: Schedule of Assessments (Phase 2, Combination of DSP-7888 Dosing Emulsion and Pembrolizumab for Ovarian Cancer)**

Period	Pre-screening	Screening period	Treatment Period (All procedure must be performed PRIOR to injection of study treatment)										Follow-up Period		Notes
			1			2			3	4	5+*	EOT (30 day after last dose)	Disease follow up**	Survival Follow up	
			1	8	15	1	8	15	1	1	1				
			0	1	2	3	4	5	6	9	12				
Scheduling Window (Days)	-	-28 to 1*	0	±2	±2	±2	±2	±2	±3	±3	±7	+7 a	±7	±14	*Procedures in screening should be completed within 28 days from Cycle 1 Day1
Study Drug Administration															
DSP-7888 Dosing Emulsion			X	X	X	X			X	X	X				
Pembrolizumab						X			X	X	X				
Administrative procedure															
HLA screening informed consent	X														
Informed Consent*		X													*Main informed consent and informed consent for future biomarker (optional) for willing participants
Inclusion and Exclusion criteria		X													
Demography and Medical History		X*													*including COVID-19 history and vaccination history
Prior and Concomitant Medications		X	X	X	X	X			X	X	X	X			
Cancer history and Cancer Prior Treatment		X													

Period	Pre-screening	Screening period	Treatment Period (All procedure must be performed PRIOR to injection of study treatment)										Follow-up Period		Notes	
			1			2			3	4	5+*	EOT (30 day after last dose)	Disease follow up**	Survival Follow up		
Treatment Cycle	Day	Week (from 1 st dose)	1	8	15	1	8	15	1	1	1					
Scheduling Window (Days)	-	-28 to 1*	0	±2	±2	±2	±2	±2	±2	±3	±3	±7	+7 a	±7	±14	
New anticancer therapy														X	X	*Every 12 weeks up to 105 weeks and/or on an ad-hoc basis for safety or regulatory purposes, or a prespecified analysis.
Safety assessment																
Physical Examination*		X	X			X				X	X	X	X			*Inspection of prior injection site will be done
Vital Sign and Weight		X*	X	X	X	X				X	X	X	X			*Height will be measured only at screening
12-lead ECG		X								X			X			
ECHO/MUGA		X														
ECOG performance status		X	X	X	X	X				X	X	X	X			
Adverse Events	X*	X**	X	X	X	X				X	X	X	X**			* SAE related to study procedure will be reported to ██████████ Safety **AE must be collected from the date of main ICF to 30 days after last dose

Period	Pre-screening	Screening period	Treatment Period (All procedure must be performed PRIOR to injection of study treatment)										Follow-up Period		Notes	

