### **8.3. Dose Modification**

Any study treatment may be interrupted at any time for any grade toxicity considered intolerable by the patient, based on the investigator's and patient's judgment.

In the case of any patient who has missed 4 or more consecutive doses of either study drug, that study drug should be permanently discontinued, but the patient may continue on the other nonmissed study drug. If the patient is experiencing clinical benefit and, in the opinion of the investigator it is in the patient's best interest to remain on study, the patient may continue treatment on a case-by-case basis, after documented discussion with the Sponsor.

Dose modification by treatment is described in the following sections.

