#### **8.3.1. DSP-7888 Dosing Emulsion Dose Modification in Phase 1b**

The dose of DSP-7888 Dosing Emulsion should be held for any Grade 3 or Grade 4 toxicity that is related to DSP-7888 Dosing Emulsion and that is present on a scheduled dosing day. Dosing may be resumed at a reduced dose once the toxicity has resolved to Grade 1 or less. If the toxicity occurs at a dose of 10.5 mg, dosing may resume at the dosage of 3.5 mg. If the toxicity occurs at a dose of 3.5 mg, dosing may resume at a dose of 1.75 mg. No inpatient dose reduction is allowed during the DLT evaluation period.

On days when DSP-7888 Dosing Emulsion is held for toxicity, nivolumab (Arm 1) or pembrolizumab (Arm 2) should be administered if scheduled for that day. If toxicities related to DSP-7888 Dosing Emulsion preclude administration of DSP-7888 Dosing Emulsion for 4 consecutive treatments, DSP-7888 Dosing Emulsion should be discontinued; and the medical monitor and Sponsor should be consulted for case review and possible approval of continuing therapy with nivolumab (Arm 1) or pembrolizumab (Arm 2) alone.

After the induction phase, dose reduction is permitted due to ISRs if the investigator or subinvestigator has judged that a dose reduction is medically required.

Patients who experience Grade 3 or higher toxicities with a DSP-7888 Dosing Emulsion dose of 1.75 mg will be removed from the study.

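### The Phase 1b End of Treatment visit is timed from the last DSP-7888 dose, so a patient who stays on the PD-1 inhibitor alone has no scheduled labs, vital signs or ECG after the last PD-1 dose

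*Protocol*

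**What the plan says.** **Visit timing.** The EOT columns of Table 7 (Arm 1) and Table 8 (Arm 2 of Phase 1b) carry the same header, "30 days after last DSP-7888 Dosing Emulsion dose", with +7 days allowed. Vital signs, hematology, chemistry, thyroid tests, urinalysis, ECG, ECHO/MUGA and a blood sample for CTL induction are marked there. The only later column is survival follow-up. A footnote asks that EOT be completed before new anti-cancer treatment. It is silent on a PD-1 inhibitor that simply carries on.

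**PD-1 treatment alone.** Section 8.3 says of a drug missed for four or more consecutive doses that "that study drug should be permanently discontinued, but the patient may continue on the other nonmissed study drug". Section 8.3.1, for Phase 1b, says that while DSP-7888 is held for toxicity "nivolumab (Arm 1) or pembrolizumab (Arm 2) should be administered if scheduled for that day". If related toxicities "preclude administration of DSP-7888 Dosing Emulsion for 4 consecutive treatments, DSP-7888 Dosing Emulsion should be discontinued", and the case review may lead to "possible approval of continuing therapy with nivolumab (Arm 1) or pembrolizumab (Arm 2) alone".

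**The other safety clocks.** Table 7 footnote p collects AEs "until 30 days after the last dose of study drug administration", and note 14 of Table 8 does the same. The SAP windows for treatment-emergent AEs (5.4.1), laboratory values (5.4.2), ECG (5.4.3) and vital signs (5.4.4) all end 30 days past the last study drug or study treatment. Table 9 (Phase 2) has "EOT (30 day after last dose" and names no drug.

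**The concern.** The visit and the analysis windows are on different clocks. They agree when both drugs stop together or DSP-7888 stops last. When DSP-7888 stops first, the visit meant to close the safety record can take place during active PD-1 treatment, and the tables provide no second visit once PD-1 treatment ends.

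Safety is the Phase 1b primary objective, and SAP Section 5 now makes the final report a safety-focused synoptic report. Its laboratory and ECG shift tables use the maximum or worst value up to 30 days past the last study drug. For these patients, the last part of that window would hold only whatever happened to be measured off schedule. Patients who stop DSP-7888 because of toxicity are among those affected.

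**Working it through.** The plan gives no figure to reproduce. The check is day arithmetic on its own intervals.

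**Inputs**
- EOT: 30 to 37 days after the last DSP-7888 dose (Tables 7 and 8).
- Nivolumab: "every 14 days (2 weeks/cycle) starting from Day 1 of Cycle 3 (Day 29") (Table 5), so every 14 days. DSP-7888 maintenance in Arm 1 is also every 14 days (Table 4).
- Pembrolizumab and Arm 2 maintenance DSP-7888: every 21 days (Tables 4 and 5).
- DSP-7888 discontinuation for missed doses: four consecutive (Sections 8.3 and 8.3.1).

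**Assumptions.** Day 0 is a last DSP-7888 dose given in maintenance. The PD-1 inhibitor then continues on schedule for k further doses. The documents give no value for k, so I use 4 to 12 as a range.

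**Formulas.** With q the interval in days, PD-1 dose i falls on day q × i, and the fourth missed DSP-7888 dose on day 4q. EOT counted from the last dose of either drug falls on days qk + 30 to qk + 37.

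| | Arm 1 (q = 14) | Arm 2 (q = 21) |
|---|---|---|
| First four PD-1 doses | days 14, 28, 42, 56 | days 21, 42, 63, 84 |
| EOT as written | days 30–37, between doses 2 and 3 | days 30–37, between doses 1 and 2 |
| Fourth missed DSP-7888 dose | day 56 | day 84 |
| EOT window closes before that by | 56 − 37 = 19 days | 84 − 37 = 47 days |
| PD-1 doses after the EOT window, k = 4 | 4 − 2 = 2 | 4 − 1 = 3 |
| PD-1 doses after the EOT window, k = 12 | 12 − 2 = 10 | 12 − 1 = 11 |
| EOT from last dose of either drug, k = 4 | days 86–93 | days 114–121 |
| EOT from last dose of either drug, k = 12 | days 198–205 | days 282–289 |

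The mismatch begins once PD-1 dosing reaches day 42, the third nivolumab or second pembrolizumab dose. With fewer doses, EOT still follows the last PD-1 dose, but by less than 30 days at the start of the window: 30 − 28 = 2 days after two nivolumab doses, or 30 − 21 = 9 days after one pembrolizumab dose.

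By the four-missed-doses route, the visit date passes before DSP-7888 is known to have ended, so a site could not follow the header prospectively.

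**What is still measured.** The Cycle 7+ column (Table 7) and the Cycle 5+ column (Table 8) schedule laboratory tests and vital signs every cycle. ECG is every third or second cycle, and ECHO/MUGA every sixth or fourth. Nothing ends these columns when the vaccine stops. However, both tables require all tests except ECG before injection of study treatment. Read across to days with PD-1 dosing only, the last scheduled laboratory and vital-sign values precede the last PD-1 dose. The last scheduled ECG can precede it by up to 2 × 14 = 28 days (Arm 1) or 1 × 21 = 21 days (Arm 2).

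**The case against.** A reader might infer that safety data are missing for the whole PD-1-alone period plus 30 days. The documents do not support that. Per-cycle assessments run on, and Section 7.3.1 asks patients who have stopped investigational product to stay on the observation schedule. The SAP windows take scheduled and unscheduled records, so all of those values count, as does the EOT visit as written.

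Nor is it right that nothing is collected after the last PD-1 dose. AEs are recorded to 30 days past the last study drug and followed to resolution, return to baseline or stability (Sections 6.1.4.5 and 11.1.2.2.1). Abnormal laboratory values meeting the criteria of Section 11.1.2.3.5 are reported as AEs. Patients who withdraw from the study are asked for the final evaluations (Section 7.3.2). The ECHO/MUGA gap has no planned analysis behind it, because SAP 5.4.1 to 5.4.4 contain none. Table 9 is not a model for Phase 1b either, since it leaves the drug unnamed.

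The situation itself is restricted. Section 6.3.1 ties combined treatment to expected benefit from DSP-7888. Section 7.3.1 lists an AE precluding DSP-7888, and withdrawn consent for any one drug, as reasons to end protocol therapy. Section 8.3.1 makes PD-1 treatment alone only a possibility after review. If protocol therapy always ended with the vaccine, the header would be largely coherent. A visit fixed to the investigational product is also a defensible choice in itself.

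All of this narrows the point. It does not remove it: Sections 8.3 and 8.3.1 still provide for PD-1 treatment alone, and SAP 5.2.6.1 allows for it by running treatment duration to the later of the last DSP-7888 or checkpoint-inhibitor dose. AE reporting does not replace scheduled tests.

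**Conclusion.** The concern holds in a limited form. In Phase 1b patients whose DSP-7888 ends before the PD-1 inhibitor, EOT as written can fall between PD-1 doses, and no laboratory tests, vital signs or ECG are then scheduled after the last PD-1 dose. What could be lost is a worst value that first appears in those final 30 days. On-treatment data and AE collection are not lost.

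The number of such patients is not given. The dose search part is complete (Section 6.1.2), so this concerns mainly the planned enrichment cohort of 10. The day counts assume a last vaccine dose in maintenance and PD-1 dosing on schedule; the range k = 4 to 12 is illustrative. This is a minor inconsistency that is worth correcting because correction is cheap.

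**What to change.** - In the EOT headers of Tables 7 and 8, count the 30 days from the last dose of either study drug (DSP-7888 or the PD-1 inhibitor), whichever is later. This matches footnote p, note 14 and the SAP windows.
- In Table 9, name the drugs to which the last dose refers.
- Reconcile Sections 6.3.1, 7.3.1, 8.3 and 8.3.1 on whether PD-1 treatment alone is possible. I take no position on that clinical rule.

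The cost is two header edits and one clarification at the next amendment. An existing visit moves and none is added. The small downside is that, in these patients, the visit and CTL sample fixed at 30 days after the last vaccine dose move too. The amendment helps only patients still on treatment. If none remain, the clinical study report should instead state the limitation and say how many patients had their EOT visit before their last PD-1 dose.
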